7.4 Reporting Procedures

When an AE or SAE is reported by a participant, we will ask for clarifying information describing the event. Any SAEs will be immediately reported to [name] and, if he is unavailable, to [name]. Reports to [name] will include a description of the event and a summary of recent contacts with the patient. This summary will include any warning signs of the adverse event, the patient's general state and any information suggesting a causal link between study participation and the event.

SAEs that are unanticipated, serious, and possibly related to the study intervention will be reported to the Independent Safety Monitor(s), IRB, and NCCIH in accordance with requirements.

- Unexpected fatal or life-threatening AEs related to the intervention will be reported to the NCCIH Program Officer, and Independent Safety Monitor(s) within 3 days of the investigator becoming aware of the event.
- Other unexpected SAEs that are related or probably study related will be reported to the IRB, NCCIH Program Officer, and Independent Safety Monitor(s) within 5 days.
- SAEs and AEs that do not meet criteria for reporting within five working days in accordance with VHA Handbook 1058.01 will be reported to the Central IRB and the Independent Safety Monitor(s), at the time of continuing review (overall total and summary of types of events that occurred) in accordance with their requirements. Such events will be reported to NCCIH on an annual basis.
- All other AEs documented during the course of the trial will be reported to NCCIH on an annual basis by way of inclusion in the annual report and in the annual AE summary which will be provided to NCCIH and to the Independent Monitors. The Independent Safety Monitor(s) Report will state that all AEs have been reviewed.

7.5 Follow-up for Adverse Events

The response to clinical emergencies will be delineated in the Service Use Agreements between the hub site and spoke for provision of SBIRT-PM. All VISN1 medical centers have emergency room facilities and a suicide prevention coordination team. If the participant's situation precludes management by spoke personnel (e.g. the Veteran is not accessible to VA staff or the site PI), the Research Assistant will immediately consult with one of the mPIs about ways to handle the situation, including calling for a police safety check on the Veteran.

7.6 Safety Monitoring

A Data and Safety Monitoring Committee (DSMC) will be appointed by NCCIH to review study progress, assess the adequacy of ongoing enrollment & site performance, ensure adequacy of data acquisition & protocol adherence and evaluate overall safety throughout trial implementation. The DSMC will meet at least annually after trial initiation. A DSMC Charter Document outlining the operating guidelines for the committee, the frequency of planned meetings and the specific data presentation format will be agreed upon during the initial meeting of the DSMC. Study reports will be created by the study data center, following a standardized format, as directed by the DSMC. The DSMC will report directly to NCCIH.

Study progress and safety will be reviewed annually during the RCT. Progress reports, including patient recruitment, retention/attrition, and AEs will be provided to the DSMB annually. This Annual Report will include a list and summary of AEs. In addition, the Annual Report will address (1) whether AE rates are consistent with pre-study assumptions; (2) reason for dropouts from the study; (3) whether all participants met entry criteria; (4) whether continuation of the study is justified on the basis that additional data are needed to accomplish the stated objectives of the study; and (5) conditions whereby the study might be terminated prematurely. The Annual Report will be sent to the Independent Monitor(s) and will be forwarded to the VA Central IRB and the NCCIH Program Officer within 1 month of each monitoring review.

8. INTERVENTION DISCONTINUATION

This study will be stopped prior to its completion if: (1) the intervention is associated with adverse effects that call into question the safety of the intervention; (2) difficulty in study recruitment or retention will significantly impact the ability to evaluate the study endpoints; (3) any new information becomes available during the trial that necessitates stopping the trial; or (4) other situations occur that might warrant stopping the trial.

9. STATISTICAL CONSIDERATIONS

9.1 General Design Issues

The pragmatic two-arm, parallel groups 36-week randomized controlled single blind trial design was selected based on findings from a completed pilot study ([name] et al., 2018). The study design parameters---components of the intervention and its duration, duration of follow-up, and effect size estimates---were largely derived from that study. Treatment-as-usual was selected as a control condition because the question to be answered by this pragmatic trial is whether the intervention is more effective than the status quo.

Our main objective is to test the effectiveness of SBIRT-PM, compared to Usual Care (UC), when delivered within a VISN1-wide hub-and-spoke network.

Hypothesis 1: SBIRT-PM will be more effective than UC in reducing pain severity as measured by the Brief Pain Inventory (primary outcome #1).

Hypothesis 2: SBIRT-PM will be more effective than UC in reducing the number of substances categorized as requiring any intervention (primary outcome #2) as identified by either self-report (ASSIST) or toxicological analysis of nail clippings.

9.2 Sample Size and Randomization

Given there are two primary outcomes (change in pain severity from the BPI, change in the number of substances whose use requires intervention based on the ASSIST), Bonferroni correction was used to generate a p-value of .025 for the sample size calculations for each outcome.

The planned (randomized) sample size is 1100 with sample selection at each site proportional to the size of the site. This sample size was based on power=.90 using alpha=.025, and an expected ES of $d=.25$ for pain severity. Breakdown as follows: 400 per group divided by '1 – loss to follow-up' (73%) = $548 \times 2 \text{ groups} = 1096$. Clustering was removed from the calculation per the advice of the PMC3 Biostatistics workgroup leadership during our protocol review. Instead, site will be controlled in analyses and a site by treatment interaction effect tested. In addition, power was increased to 90% based on their advice.

The planned sample size allows for 27% attrition. Values are based on previous related work and our 12-week pilot study. In Poisson modeling of our pilot data, SBIRT was associated with a baseline-adjusted relative rate of pain-related appointments attended (a proposed mediator of SBIRT-PM) of RR (Exp(B))=1.6.

For substance use, the proportion converting to low risk on at least one substance in the treatment group was estimated as 27% and in UC as 10%. Attrition was set at 27%. For 90% power (alpha=.025), the calculations resulted in sample size of 128 per group divided by '1 – loss to follow-up' (73%) = $176 \times 2 \text{ groups} = 352$ as the total sample size. Given the sample size required for the pain outcome, a small effect size (absolute value of 6% between groups) would be detectable for the substance use outcome with 90% power. In the UG3 pilot study, 67% of the participants at baseline self-reported on the ASSIST a level of risky substance use (either alcohol, tobacco or other drugs) that would require intervention and 33% reported risky alcohol use. Projected to the full trial, this suggests 737 participants are likely to have a clinically significant problem with at least one substance and 357 will have a problem with

alcohol. Thus, we will have an adequate sample in the UH3 RCT to detect changes in our primary substance use outcome.

Treatment Assignment Procedures

The unit of randomization is participant. Participants will be randomized to SBIRT or Usual Care using a computerized urn randomization program within each site to increase the likelihood of balanced allocation of participants to the two interventions on several covariates: sex (male/female), race (White, Black), ethnicity (Hispanic/Non-Hispanic), and self-reported illicit drug use within 90 days (Yes/No). All randomization will be done by the Project Director.

Urn randomization preserves randomization as the primary basis for assignment to treatment and is less susceptible to experimenter bias or manipulation of the allocation process by staff than is balancing. The urn randomization algorithm allows probability of assignment to fluctuate as a function of the degree of covariate imbalance. As a study's sample size increases, urn and simple randomization converge because the treatment assignment probabilities under urn randomization converge asymptotically to the simple randomization probabilities.

Blinding

Research assistants who collect study data will be blind to participants' treatment assignment. Veterans will be instructed during the assessments not to tell the research assistant if they are receiving study counseling. To determine if the blind was maintained, the research assistant will be asked to what condition each Veteran was assigned.

The PIs and Project Director will not be blind to randomization, as they will be assigning study therapists to participants randomized to the treatment condition, reviewing counseling sessions for quality/fidelity, and conducting monthly supervision with study counselors. The statistician has no contact with the study veterans; she will not be blinded.

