9.5 Outcomes

9.5.1 Primary Outcome

The two primary outcomes are pain severity as measured by the BPI and the number of substances above the “no intervention” threshold in the ASSIST. We initially planned that when a positive toxicology result disagrees with a self-report of no use, the middle value on the ordinal scale (the indication to receive brief intervention) would be derived and used as the primary substance use outcome. However, only 64% of participants returned nail samples at baseline, and this percentage dropped to 58% and 49% at week 12 and 36, respectively, among participants with completed ASSIST assessments. Further, depending upon the substance and timepoint, between 43% and 48% of participants self-reporting a level of substance use that does not require an intervention, the group whose substance use classification would change with positive nail toxicology, did not have toxicology results. Given the amount of missing toxicology data and that nails do not measure intervention need directly like the ASSIST, we plan to base our primary substance use outcome on the ASSIST measure only. This change does not compromise our estimated power since the number of participants self-reporting a level of risky substance use that requires an intervention on the ASSIST (N=571) exceeds our assumed total sample size for this outcome (N=352) used in power analyses. The BPI and ASSIST are collected at baseline, week 12 and week 36.

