9.6 Data Analyses

All variables (Intervention, covariates and outcomes) will be described with the use of the approximate summary statistics (mean, median, interquartile range, and percent). Multivariate models will be used following the examination of bivariate tests of outcomes by intervention group. A successful outcome will be either a reduction in pain severity or number of substance use above the “no intervention” threshold in the ASSIST or toxicological analysis of nail clippings. The model type will be selected based on meeting of modeling assumptions including the outcome distribution; Potential models will include linear and non-linear mixed-effects (Poisson (with over-dispersion), negative binomial, binary outcome) regression modeling. If there is a large skew with many zeros (which is quite possible where the outcome is change in the number of substances no longer needing intervention), we will use a negative binomial. If the distribution is a combination of 0's (no change) and 1's (change to level of “no need for intervention” in one substance) with very few outcomes greater than 1, a binomial distribution will likely be used. A Poisson model will be used if there are very few successes and they have a Poisson distribution.

These common rules will be used for guidance:

- Poisson distribution, if mean = variance
- Binomial distribution, if mean > variance
- Negative binomial distribution, if mean < variance

The covariance structures will be explored to determine which (unstructured, compound symmetry, autoregressive) is the most appropriate in mixed models. Selection will be based on the lowest AIC. An intervention by time interaction will be tested in the models – this will show the effect of the intervention on the outcome compared to controls.

Change in Pain: We anticipate using linear mixed-effects modeling to test the effect of SBIRT-PM on the 12-week value of the BPI, if it is a normally distributed outcome. We will in addition test simultaneously the unique effects of treatment on pain outcomes at week 12 and week 36, controlling for baseline differences, and test the equality of these parameters using the Wald test.

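### Section 9.6 sets no alpha or multiplicity rule for the two final primary tests; stating Holm there would be a cheap improvement on carrying the .025 sizing level into both

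*Combined protocol and SAP*

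**What the plan says.** Section 9.1 sets out two separate hypotheses, one for pain and one for substance use. Section 9.5.1 confirms the pair: "The two primary outcomes are pain severity as measured by the BPI and the number of substances above the" no-intervention level of the ASSIST.

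The only multiplicity adjustment in the document is in section 9.2: "Bonferroni correction was used to generate a p-value of .025 for the sample size calculations for each outcome". For pain, the same section adds: "This sample size was based on power=.90 using alpha=.025, and an expected ES of $d=.25$ for pain severity". That leads to 400 evaluable per group, 548 per group after 27% loss, 1096 in total, and "The planned (randomized) sample size is 1100". For substance use, 27% against 10% at the same alpha and power gives 128 evaluable per group and 352 in total.

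Section 9.6 describes the models and treats the two outcomes as alternatives: "A successful outcome will be either a reduction in pain severity or number of substance use above" the threshold. It gives no alpha and no multiplicity procedure for the final primary tests. Section 9.4 plans no interim analysis, so no alpha is spent elsewhere.

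**The concern.** A reader of sections 9.2 and 9.6 would most naturally carry .025 into both final tests. That is valid, but with two hypotheses it is stricter than necessary once one has been rejected. Holm tests the smaller p-value at .025 and, if that is significant, the other at .05. It controls the family-wise error at .05 under any correlation between the outcomes, and it rejects everything that Bonferroni rejects.

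What is at stake is the second claim. Suppose the ASSIST result is clearly positive and pain gives p=.03. Pain would miss a fixed .025 and pass under Holm, and the plan does not say which rule applies. Choosing after seeing the p-values would be a post hoc decision, and the statistician is not blinded (sections 6.2.3 and 9.2).

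**Working it through.** **Inputs.** From section 9.2: alpha .025 per outcome, power .90, d=.25, 400 per group, 27% loss, 27% against 10% for substance use. From section 9.5.1: 571 participants at risk on the ASSIST. The plan does not state sidedness. Two-sided is inferred because one-sided .025 gives 337 and 108 per group, which do not match the plan. The correlation between the two test statistics is not given either; it is assumed and varied from 0 to 0.6.

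**1. The plan's own sizes.** Critical values are 2.241 (two-sided .025), 1.960 (two-sided .05) and 1.282 (90% power).

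- Pain: n = 2(2.241 + 1.282)² / .25² ≈ 398 per group (plan: 400). 400/.73 = 548, and 548 × 2 = 1096.
- Substance use, pooled two-proportion formula without continuity correction: 128 per group (plan: 128). 128/.73 = 175.3, rounded up to 176, and 176 × 2 = 352.

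Both reproduce. The split uses 2 × .025 = .05.

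**2. Pain power at each threshold, 400 per group.** Power = Φ(.25√(400/2) − z), and .25√200 = 3.536.

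- At .025: Φ(3.536 − 2.241) = 90.2%.
- At .05: Φ(3.536 − 1.960) = 94.2%.

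The planned 90% is therefore already met at .025. The 94.2% is reached only if the ASSIST test is certain to succeed.

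**3. Chance of at least one success.** Holm's first step is also .025, so this probability is the same under both procedures. The gain is zero.

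**4. Marginal pain power under Holm.** Set pain power at .025 to exactly 90%. Its power at .05 is then Φ(1.282 + 2.241 − 1.960) = 94.1%. With independent statistics,

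power = .900 + (.941 − .900) × (ASSIST power at .025).

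For ASSIST power of 50% this is .900 + .041 × .50 = .9205. For correlated statistics the last term comes from a bivariate normal distribution.

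| ASSIST power at .025 | Correlation 0 | 0.3 | 0.6 |
|---|---|---|---|
| 99.99% | 94.10% | 94.10% | 94.10% |
| 90% | 93.69% | 93.34% | 92.89% |
| 50% | 92.05% | 91.35% | 90.59% |
| 20% | 90.82% | 90.38% | 90.07% |

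**5. Chance of winning both, each with 90% power at .025.** With independence, Bonferroni gives .90 × .90 = 81.0%. Holm gives 2(.941 × .90) − .81 = 88.4%. At correlation 0.3 the figures are 82.2% and 88.9%; at 0.6 they are 83.9% and 89.7%.

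**6. Where the plan's assumptions put ASSIST power.** Applying 27% loss to the 571 at-risk participants leaves 571 × .73 / 2 ≈ 208 per arm. At 27% against 10% and alpha .025, a two-proportion test has 98.9% power. Pain power under Holm with 400 per arm (independence) would then be 90.2 + (94.2 − 90.2) × .989 ≈ 94.2%.

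**7. Family-wise error.** Simulation with both nulls true, and with one null true, at correlations 0 and 0.5, gave 4.5% to 5.0% under Holm.

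**The case against.** The strongest reply is that nothing in the plan is wrong. Bonferroni is valid, the sample size delivers its 90% at .025, each conclusion stands without reference to the other outcome, and 97.5% intervals match the tests directly. All of that stands, and it is why this is an improvement and not a correction.

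Three stronger readings are tempting, and the documents do not support them.

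- *The plan fixes .025 for the final tests, so pain at p=.03 would be declared a failure.* Section 9.2 ties .025 to the sample size calculations, and section 9.6 names no threshold. Holm is not excluded.
- *Power is given away for nothing, worth about 18% more participants.* The ratio ((2.241 + 1.282)/(1.960 + 1.282))² = 1.18 assumes that ASSIST always succeeds, so it is an upper limit. Bonferroni's simpler intervals and independent conclusions also have some value.
- *Pain would nearly always be tested at .05.* That rests on the 98.9% in step 6, which needs the 27% against 10% effect to hold and treats the analysis as a comparison of proportions among baseline risky users. Section 9.6 plans a count model, with risk sets as only one subset of analyses.

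Two practical objections also stand. Holm needs one p-value per outcome, and section 9.6 offers several: an intervention-by-time interaction, the week-12 BPI value, joint week-12 and week-36 effects, and a count model chosen from the data. Timing matters too. Section 9.5.1 already reports week-36 nail return rates, and section 10.2 has the project statistician checking files monthly, partly to monitor differences between treatment types. The documents cannot confirm that no arm-level outcome result has been seen. Since no final threshold is stated, adopting Holm relaxes no written analysis rule, but the date of the decision should be recorded.

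**Conclusion.** The point holds as a specification gap with an inexpensive improvement. Section 9.6 should state the alpha and multiplicity rule for the two primary tests, and Holm is the better choice if power for the second claim, or for both, matters. Section 9.1 frames them as two separate hypotheses, so it does.

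The size is modest and conditional. At 400 per arm the gain in pain power is at most about 4 points, about 3 to 4 if ASSIST power is 90%, about 1 to 2 if it is 50%, and under 1 if it is 20%. The gain for winning both is about 6 to 7 points when each outcome has 90% power. There is no gain for at least one success. These figures assume two-sided tests, d=.25, the planned 27% loss and a correlation between 0 and 0.6.

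**What to change.** Add to section 9.6, before any arm-level outcome analysis: the two primary hypotheses, each with one named primary test and time point, are tested by the Holm procedure at two-sided family-wise .05. The smaller p-value is compared with .025 and, if significant, the other with .05. Report 97.5% confidence intervals for both effects alongside, and record the date on which the rule was fixed.

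Keep the .025 sizing and N=1100. Sizing at .025 remains the safe choice under Holm, because an outcome reaches the .05 threshold only after the other has succeeded.

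The change costs a sentence or two plus the naming of one test per outcome. It adds no participants and keeps the family-wise error at .05. The drawbacks are that simultaneous intervals matching Holm are less simple than Bonferroni's, so the 97.5% intervals may not agree with a second-step rejection, and that the second conclusion depends on the first.

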Change in Substance Use: We anticipate using non-linear mixed-effects (Poisson, negative binomial, binary outcome as discussed above) regression modeling to test the effect of SBIRT-PM on the number of substances requiring intervention (according to the ASSIST), a count outcome. One subset of analyses will use risk sets

(at least 1 substance at baseline, at least 2 substances at baseline, etc.) to analyze substance risk changes in substance users. We will also test the equality of treatment effects at weeks 12 and 36 as described above.

We have identified stratification variables to account for error variance as a recommended good practice. Key covariates to be included in the model are depression, TBI, and mental health diagnoses (grouped into multiple more homogenous groupings, such as mood and psychotic disorders) as these are highly related to pain perception and substance abuse as well as the urn covariates—namely sex, race, ethnicity, self-reported illicit drug use and site. The strata used for the urn randomization are only to better ensure balance on key characteristics. Their main effects will not be interpreted in the analysis, though they will be examined as potential modifiers of the intervention effect. We will also consider as potential covariates: distance to nearest VA medical center, number of pain treatment modalities used at baseline, reasons patient might drop out of the study, and the probability of withdrawal. Opioid-use will be examined as a mediator as well as a tertiary outcome. Actual participation in SBIRT-PM (Y/N) will be examined as a mediator of response.

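### Section 9.2 claims 90% power for a 6-point difference in the substance-use primary outcome; on the section's own inputs power is about 61%, and the increase detectable with 90% power is about 8.7 points.

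*Combined protocol and SAP*

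**What the plan says.** Section 9.2 splits alpha between the two primary outcomes: "Bonferroni correction was used to generate a p-value of .025 for the sample size calculations for each outcome". The trial is sized on pain (d = .25, 90% power). This gives 400 evaluable per group, inflated for 27% loss to 548 randomized per group ("Breakdown as follows: 400 per group divided by" 0.73).

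The substance-use outcome is sized as a comparison of proportions: "the proportion converting to low risk on at least one substance in the treatment group was estimated as 27% and in UC as 10" percent. The result is stated as "For 90% power (alpha=.025), the calculations resulted in sample size of 128 per group", which becomes 176 per group and 352 in total after the same attrition allowance.

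The section then says that, because the pain outcome needs the larger sample, "a small effect size (absolute value of 6% between groups) would be detectable for the substance use outcome with 90% power". It gives no other control rate for this sentence, and it never states whether tests are one- or two-sided.

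Hypothesis 2 in section 9.1 sets the direction of benefit: "SBIRT-PM will be more effective than UC in reducing the number of substances categorized as requiring any intervention".

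**The concern.** For a given n, the detectable difference between two proportions depends on the control rate and the direction. With a 10% control rate and 400 per group, 6 points upward looks too small to carry 90% power at alpha .025.

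This is the plan's only statement of how sensitive the trial is, on its second primary outcome, to an effect smaller than the assumed 17 points. A reader of a null or small substance-use result would conclude from it that a true 6-point benefit had only a 10% chance of being missed. The section goes on to call the sample adequate for this outcome.

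**Working it through.** **Inputs, all from section 9.2:** UC rate 0.10; SBIRT-PM rate 0.27 for the original sizing; alpha .025; power 90%; 400 evaluable per group. Two-sided testing is inferred in step 1. Normal quantiles: z(1 − .025/2) = 2.2414 and z(.90) = 1.2816.

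**Formulas (pooled-variance normal approximation, equal groups).** With p̄ = (p1 + p2)/2, A = √[2p̄(1 − p̄)], B = √[p1(1 − p1) + p2(1 − p2)] and Δ = |p1 − p2|:

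- n per group = (2.2414·A + 1.2816·B)² / Δ²
- power = Φ[(Δ√n − 2.2414·A) / B]

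**1. Reproduce the plan's own figures.**

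- 27% vs 10%: A = 0.5491, B = 0.5358. n = (1.2308 + 0.6867)² / 0.17² = 3.677 / 0.0289 = 127.2, so 128, as stated. One-sided .025 would give 108, so the section used a two-sided test. 128/0.73 rounds up to 176 per group, or 352 in total.
- Pain: n = 2(2.2414 + 1.2816)² / 0.25² = 397.2, against 400 stated. 400/0.73 = 548.

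**2. Power for 6 points upward from 10% at 400 per group.** For 10% vs 16%, A = 0.4756 and B = 0.4737. Power = Φ[(0.06 × 20 − 2.2414 × 0.4756) / 0.4737] = Φ[(1.2000 − 1.0660) / 0.4737] = Φ(0.283) = 61.1%. Cross-checks: arcsine 61.7%, unpooled variance 61.5%, simulation of 200,000 trials 61.5%.

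**3. Sample size that 6 points would need.** n = (1.0660 + 0.6071)² / 0.06² = 2.799 / 0.0036 = 778 evaluable per group.

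**4. Increase detectable with 90% power at 400 per group.** Setting power to 0.90 and solving gives 8.7 points (10% vs 18.7%).

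**5. Alternative readings.**

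| Reading | Power for 6 points | Detectable at 90% | Fit with the section |
|---|---|---|---|
| 400/group, two-sided .025, increase | 61% | 8.7 | Section's inputs |
| 548/group (no attrition) | 76% | 7.3 | Ignores the 27% loss |
| 400/group, two-sided .05 | 71% | 7.9 | Not the stated alpha |
| 400/group, decrease from 10% | 86% | 6.3 | SBIRT-PM worse than UC |
| 548/group, one-sided .05 | 91% | 5.9 | Neither the stated alpha nor the attrition |
| 800/group | 91% | 5.9 | 800 is the evaluable total |

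At 400 per group and two-sided .025, power for +6 points at other UC rates is 91% at 3%, 81% at 5%, 68% at 8% and 49% at 15%. It reaches 90% only at a UC rate of about 3.2% or lower.

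**6. If the 10% and 27% apply only to participants with a risky substance at baseline.** The section does not state the denominator, so these are conditional figures for 10% vs 16% within that subset:

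| Subset | Evaluable per group | Power for 6 points | Detectable at 90% |
|---|---|---|---|
| 737 projected (section 9.2), 27% loss | 737 × 0.73 / 2 = 269 | 43% | 10.9 |
| 571 observed (section 9.5.1), 27% loss | 571 × 0.73 / 2 = 208 | 34% | 12.7 |
| 571, if already after loss | 571 / 2 = 285.5 | 46% | 10.6 |

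If the subset rate is instead diluted over the whole sample, the UC rate is 0.67 × 10% = 6.7%. At 400 per group, 6.7% vs 12.7% then has 73.5% power, with 7.6 points detectable. The assumed 27% vs 10% effect keeps about 99% power even at 208 per group.

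**The case against.** The sentence names no control rate or direction, so the mismatch depends on carrying the 10% forward. Solving downward from 10% at 400 per group gives 6.28 points, which rounds to 6, so the figure may simply be the lower root reported without its sign. That is a plausible origin, though the documents do not confirm it. It does not rescue the claim: a fall in conversion means SBIRT-PM doing worse than UC, and exactly 6 points downward has 86% power, not 90%.

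A second objection is that 8.7 may also be wrong as a replacement. Only participants with a risky substance at baseline can convert, and sections 9.2 and 9.5.1 both judge adequacy by the number of such participants. If the rates belong to that subset, 400 per group is the wrong n. This stands, and it is why the denominator has to be stated before a figure is fixed. It makes the stated 6% less tenable, because every subset figure in step 6 is larger than 8.7.

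Third, the planned analysis is not a simple comparison of proportions. Section 9.6 anticipates mixed-effects "regression modeling to test the effect of SBIRT-PM on the number of substances requiring intervention (according to the ASSIST), a count outcome", with covariates and two follow-ups, and its power could be higher or lower. That is a fair caveat on all the figures here, but the plan sized this outcome with the same binary approximation.

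Finally, the sentence sets nothing in the design, and interpretation of a null result would rest mainly on the confidence interval. This limits the seriousness of the error but does not make the figure correct.

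**Conclusion.** The stated 6 points at 90% power does not follow from the section's inputs in the hypothesised direction. With UC conversion of 10%, two-sided alpha .025 and 400 evaluable per group, power for a 6-point increase is about 61%, so the chance of missing it is about 39%. The increase detectable with 90% power is about 8.7 points. No reading consistent with the text reaches the stated figure.

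The result rests on three assumptions: the 10% applies to all 400 per group, the test is two-sided (inferred from the 128), and the binary approximation is used. Without attrition the figures are 76% and 7.3 points; within baseline risky users they are 34–46% and 10.6–12.7 points.

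The error is confined to this sentence. The 1100, the 352 and the comparison of 571 with 352 in section 9.5.1 are not in question. It should be fixed because it misstates sensitivity on a primary outcome.

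**What to change.** Replace the sentence in section 9.2 with one that gives control rate, direction, sidedness and evaluable n. For example, if the rates apply to all randomized participants:

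> *With UC conversion of 10%, two-sided alpha .025 and 400 evaluable participants per group, an increase of about 8.7 percentage points (10% vs 18.7%) would be detectable with 90% power.*

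State whether the 10% and 27% refer to all randomized participants or only to those with at least one risky substance at baseline. If the latter, give the subset figures instead, with the assumed number evaluable and whether 571 is before or after loss to follow-up. If a different control rate was intended, state it and recompute. Add that the figures are for the binary conversion approximation and not for the count model in section 9.6.

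The cost is wording only. The stated sensitivity becomes less favourable; no sample size changes.
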